In the safety and tolerability Phase 2 ARTS study ([Pitt et al. 2013](#)) finerenone in daily doses ranging from 2.5 to 10 mg was tested in comparison to placebo and spironolactone (25-50 mg) in patients with HFrEF and mild to moderate kidney dysfunction. Results showed trends towards greater reduction in NT-proBNP levels with finerenone 10 mg compared with spironolactone, whereas increases in serum potassium were statistically significantly lower in finerenone arms compared to spironolactone. Moreover eGFR decline was smaller and incidence of worsening renal function was lower in all finerenone arms compared to spironolactone. Adverse events were reported in 79.4% of patients in the spironolactone arm and 53.1% in the highest dose finerenone arm which was comparable with the placebo group rates (50.8%).

In the dose finding Phase 2b ARTS-HF study in patients with worsening HFrEF and T2D and/or chronic kidney disease (CKD) ([Filippatos et al. 2016](#)) finerenone showed a decrease in NT-proBNP >30% in similar proportion of patients to that of eplerenone. However,

finerenone starting at the dose of 5-15 mg OD was observed to reduce CV hospitalization and death from any cause to a greater extent compared to eplerenone, whereas the finerenone dose of 10-20 mg was associated with the lowest rates of the composite clinical endpoint. Rates of hyperkalaemia defined as potassium  $\geq 5.6$  mmol/L any time post baseline in the finerenone dose of 10-20 mg (3.6%) were comparable to those in the eplerenone arm (4.7%).

Details of the results of the clinical and non-clinical development studies conducted with finerenone can be found in the Investigator Brochure.

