**Table 6–1 Dosage of Study Intervention for Administration**

eGFR value at the Baseline Visit, based on local laboratory results:	eGFR 25 to ≤60 mL/min/1.73m 		eGFR >60 mL/min/1.73m 	
Participant randomized to group:	Finerenone	Placebo	Finerenone	Placebo
Starting dose:	10 mg finerenone OD	Placebo OD (Dose Level 1)	20 mg finerenone OD	Placebo OD (Dose Level 2)
Maintenance dose:	20 mg finerenone OD	Placebo OD (Dose Level 2)	40 mg finerenone OD	Placebo OD (Dose Level 3)
Minimum dose after down-titration:	10 mg finerenone OD	Placebo OD	10 mg finerenone OD	Placebo OD
Maximum dose after up-titration:	20 mg finerenone OD	Placebo OD	40 mg finerenone OD	Placebo OD
Study intervention intake	One tablet of study intervention OD, preferably in the morning at approximately the same time each day. Note: Study intervention will be administered at home, except on the day of the first PK visit when the tablet will be taken at the study site			
Missed intake	
 
If discovered within 16 hours after the scheduled time, the participant should take one tablet of study intervention as soon as possible
 
If discovered >16 hours after the scheduled time, this will be considered to be a 'missed' dose and the participant should wait and take the next tablet of study intervention at the usual (scheduled) time.
 
			
Up-titration of dose	
Finerenone
 
 
Up-titrate study intervention to the next possible higher dose based on serum/plasma potassium level
 
eGFR decrease is <30% compared to last scheduled visit.
 
 
Placebo
 
 
Sham-titrate.
 
			
Down-titration of dose	
 
If potassium ≥5.5, down-titrate to the next lower dose level in a step-wise manner (dose level 2 to 1, or dose level 3 to 2)
 
If at dose level 1, interrupt study intervention treatment; study intervention should be re-introduced at dose level 1 as soon as the investigator considers it to be medically justified without compromising safety
 
If in the opinion of the investigator, the participant cannot tolerate the maximum dose level of study intervention, the study intervention dose may be reduced to the next lower dose level.
 
			

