### Local Laboratory Assessment

Blood safety samples will be taken from the Screening Visit onwards for analysis at the local laboratory.

- The following clinical chemistry parameters must be measured and the values documented in the eCRF
  - Serum/plasma creatinine (eGFR will be calculated automatically in the eCRF using the CKD-EPI formula)
  - Serum/plasma potassium.

From visit 2 (Month 1) onwards, study participants may have their local laboratory assessments taken up to 3 days prior to the study visit.

Potassium values should be recorded using a single decimal point (e.g. 4.5 mmol/L or mEq/L). In the event of hyperkalemia, please see [Table 6–2](#) for guidance.

Up-titration or down-titration of the study intervention will be based on local potassium results and must be documented in the eCRF. Down-titration of the study intervention should occur primarily for safety reasons but can also be done for exceptional logistical reasons (e.g. study intervention supply issue).

Additionally, at screening, BNP or NT-proBNP can be measured if not available from clinical medical records.

In women of childbearing potential, a pregnancy test will be performed locally, at screening and baseline. Further pregnancy tests should be performed in participants of childbearing potential as required by national/institutional regulations (e.g. at every visit). At any time during study participation, additional pregnancy testing should be performed upon suspicion of pregnancy. Both serological and urine tests are acceptable.

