#### 9.4.2 Safety Analyses

All safety analyses will be performed on the SAF.

The following safety procedures and variables will be assessed during the study:

- SAEs and AEs leading to discontinuation of treatment with study intervention
- Change in body weight from baseline
- Change in serum potassium from baseline
- Number of participants with hyperkalemia (serum potassium  $\geq 5.5$  mmol/L)
- Number of participants with severe hyperkalemia (serum potassium  $\geq 6.0$  mmol/L)
- Number of participants with hospitalization for hyperkalemia
- Number of participants permanently discontinuing study intervention due to hyperkalemia
- Change in vital signs (heart rate, SBP and DBP) from baseline
- Change in renal function measured by eGFR (CKD-EPI formula) change from baseline
- Number of participants with hospitalization for worsening of renal function
- Number of participants permanently discontinuing study intervention due to worsening of renal function
- Changes in laboratory values from baseline.

An overall summary of all AEs and treatment emergent AEs (TEAEs) will be generated by treatment group.

The number and percentage of patients with TEAEs, post-treatment AEs occurring more than 3 days after last intake of study intervention, treatment-emergent SAEs, treatment-emergent study intervention-related AEs, treatment-emergent study intervention-related SAEs, TEAEs causing premature and permanent discontinuation of study intervention, treatment-emergent non-serious AEs, TEAEs by maximum intensity, drug-related TEAEs by maximum intensity will be summarized by treatment group using MedDRA terms grouped by Primary System Organ Class and Preferred Term.

The number of patients with treatment-emergent (until 3 days after last study intervention administration) abnormal laboratory values above or below the normal range will be tabulated by the laboratory parameter and treatment group.

Summary statistics including changes from baseline will be calculated by treatment group and visit for all quantitative laboratory parameters, i.e. for hematology, clinical chemistry and urinalysis. Geometric statistics and ratios to baseline will be presented for urinary albumin-to-creatinine ratio (UACR), creatinine, and NT-proBNP, instead of arithmetic statistics with changes from baseline. For eGFR the relative change will be displayed in addition to the absolute change from baseline.

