Summary statistics for serum potassium, eGFR, and serum creatinine will also be repeated by treatment group and visit separately for each level of the stratification factors (region and LVEF).

The following special safety parameters will be further assessed by displaying the number and percentage of patients with safety events as described below by treatment group, visit, and for

any time on treatment (including unscheduled assessments) and until 3 days after last study intervention administration. This will also be performed by stratification factors. The summaries will be provided for the number and percentage of patients with:

- Absolute value of serum potassium  $>5.0 \text{ mmol/L}$ ,  $\geq 5.5 \text{ mmol/L}$  and  $\geq 6 \text{ mmol/L}$
- Relative decrease from baseline in eGFR of  $\geq 25\%$ ,  $\geq 30\%$ ,  $\geq 40\%$ ,  $\geq 50\%$  and  $\geq 57\%$
- Absolute value of eGFR  $<30 \text{ mL/min/1.73 m}^2$
- Increase from baseline in serum creatinine  $>0.3 \text{ mg/dL}$  and  $>0.5 \text{ mg/dL}$ .

The percentage of patients with the respective events (non-stratified) at any time on treatment (including unscheduled assessments) and until 3 days after last study intervention administration will be compared between the finerenone and placebo groups by applying separate exploratory  $\chi^2$  tests with continuity correction. If the expected number of patients in at least 1 cell of the 2x2 contingency table is  $<5$ , Fisher's exact test will be applied instead of the  $\chi^2$  test. Estimates and two-sided 95% confidence intervals will be provided for each treatment group and the treatment differences. Clopper-Pearson confidence intervals will be calculated for each treatment group, while for treatment differences the exact unconditional confidence limits will be calculated.

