6.4.2 Laboratory Parameters

Generally, only central laboratory measurements will be used for analyses. The only exception is for hematology, where a few countries have the possibility to use local labs in exceptional circumstances (e.g. logistical challenges due to global pandemic, natural disaster, or regional crisis). These local measurements will also be used for the analysis.

The number of participants with treatment-emergent (after the first dose of study drug and up to 3 days after last dose of study drug) abnormal laboratory values above or below the normal range will be tabulated by the laboratory parameter and treatment group.

Summary statistics including changes to baseline will be calculated by treatment group and visit for all quantitative laboratory parameters, e.g. for hematology, NT-proBNP, high sensitive troponin T (hs-TNT), clinical chemistry and urinalysis. Geometric statistics and ratios to baseline will be presented for urinary creatinine, albumin and UACR and NT-proBNP instead of arithmetic statistics with changes from baseline. For eGFR the relative change will be displayed in addition to the absolute change from baseline. Graphical displays will be provided for change from baseline and ratio to baseline by visit, respectively.

Proportion of patients with available and missing measurements will also be displayed.

Summary statistics for serum potassium, eGFR, NT-proBNP and serum creatinine will also be repeated by treatment group and visit separately for each level of the stratification factors.

The following special safety parameters will be further assessed by displaying the number of participants with safety events as described below by treatment group, visit and for any time treatment-emergent (including unscheduled assessments) and up to 3 days after last study drug administration. This will also be performed by stratification factors. The summaries will be performed for the number of participants with:

- Absolute value of serum potassium >5.0 mmol/L, >5.5 mmol/L (hyperkalemia), >6.0 mmol/L (severe hyperkalemia) and >7.0 mmol/L
- Relative decrease from baseline in eGFR of $\geq 25\%$, $\geq 30\%$, $\geq 40\%$, $\geq 50\%$ and $\geq 57\%$, also sustained decrease over 4 weeks
- Absolute value of eGFR < 30 ml/min/1.73m²
- Increase from baseline in serum creatinine >0.3 mg/dL and >0.5 mg/dL.

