Time to first occurrence of a new composite renal endpoint including sustained decrease in eGFR $\geq 57\%$ relative to baseline, mean rate of change in eGFR slope, and change in UACR from baseline are included as new exploratory endpoints and respective analyses of these endpoints are specified.

Additional model specification is included for the repeated measures model of the change in eGFR and UACR.

Exchanging analysis of AEs by SMQs with MLGs.

Handling of SAE and outcome events for Japan and India have been clarified.

Inclusion of analyses for hyperkalemia and acute renal failure.

Clarification of derivation of incidences per 100 person-years.

Handling of local hematology measurements due to local protocol amendment has been clarified.

Revision of cutoffs for special safety parameters.

Listing further safety variables in line with protocol.

Inclusion of further analyses for COVID-19 related issues.

Inclusion of analyses due to regional crisis between Russia and Ukraine.

A new section on document history and changes is included as this is required to document respective changes from the first version.

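### SAP 6.4.2 labels potassium >5.5 and >6.0 mmol/L as hyperkalemia and severe hyperkalemia, where protocol Amendment 2 section 9.4.2 uses ≥5.5 and ≥6.0; the inclusive counts are not tabulated and no reason is given

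*SAP*

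**What the plan says.** Protocol Amendment 2, section 9.4.2, lists two laboratory-defined safety variables: "Number of participants with hyperkalemia (serum potassium" ≥5.5 mmol/L), and "Number of participants with severe hyperkalemia (serum potassium" ≥6.0 mmol/L). The special safety parameters in the same section repeat both inclusive cuts: "Absolute value of serum potassium" >5.0, ≥5.5 and ≥6 mmol/L.

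SAP section 6.4.2 has the matching list. After a >5.0 row it gives ">5.5 mmol/L (hyperkalemia), >6.0 mmol/L (severe hyperkalemia) and >7.0 mmol/L". It compares the arms on these events with explorative χ² or Fisher tests and gives 95% confidence intervals for each arm and for the difference.

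The one trace of a change is in SAP section 7.1 (version 1.0 to 2.0): "Revision of cutoffs for special safety parameters". It names no parameter, value or reason. Section 7.2 (version 2.0 to 3.0) does not mention potassium cut-offs.

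SAP section 1 says the plan is based on a protocol dated 26 OCT 2022. The protocol reviewed here is Amendment 2 of 16 MAY 2022.

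**The concern.** Protocol section 2.3 calls hyperkalemia an important identified risk. With the SAP followed as written, the table row called hyperkalemia counts something other than the Amendment 2 variable of that name, and the same holds for severe hyperkalemia. A participant whose highest value is exactly 5.5 or 6.0 loses the Amendment 2 label. The two variables named in section 9.4.2 would go unreported, and a reader comparing the report with that section would find a different quantity under the same word.

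Other entries in SAP section 7.1 are more explicit. The endpoint changes are marked as following the protocol, and the change of model for total HF events is identified as differing from the protocol, with its reason. The cut-off entry has neither.

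**Working it through.** No planned figure is at issue, so there is none to reproduce. The check compares the texts and then bounds the size.

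**1. The definitions side by side**

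| Row | Protocol Amendment 2, 9.4.2 | SAP 6.4.2 |
|---|---|---|
| Lowest | >5.0 | >5.0 |
| Hyperkalemia | ≥5.5 | >5.5 |
| Severe hyperkalemia | ≥6.0 | >6.0 |
| Highest | none | >7.0 |

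**2. Can the inclusive counts be recovered from the SAP rows?** No. A participant with a maximum of exactly 5.5 appears in the >5.0 row but not the >5.5 row, mixed with maxima above 5.0 and below 5.5. A maximum of exactly 6.0 is likewise mixed with other values between 5.5 and 6.0.

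**3. Direction.** Everyone above a cut is also at or above it, so the strict percentage cannot exceed the inclusive one in either arm. The between-arm difference changes by the arms' difference in the share sitting exactly at the cut:

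difference(>) = difference(≥) − (finerenone share at the cut − placebo share at the cut).

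**4. Size, under assumptions.** The documents give neither a potassium distribution nor the precision of central values. "Potassium values should be recorded using a single decimal point" is an instruction for local laboratory values, and the analysis uses central ones. The model assumes:
- one post-baseline value per participant, normally distributed
- placebo mean 4.3, 4.4 or 4.5 and SD 0.40, 0.45 or 0.50 mmol/L
- finerenone shift +0.1 or +0.2 mmol/L (protocol section 4.3 expects changes of 0.1 to 0.2)
- rounding half-width h = 0.05 for one decimal or 0.005 for two.

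P(≥c) = 1 − Φ((c − h − mean)/SD) and P(>c) = 1 − Φ((c + h − mean)/SD).

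Across the 3 × 3 × 2 = 18 combinations:

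| Cut | Decimals | Fall in absolute difference | Risk ratio(>) ÷ risk ratio(≥) |
|---|---|---|---|
| 5.5 | one | 29.9–51.1% | 1.036–1.122 |
| 5.5 | two | 3.5–6.9% | 1.004–1.012 |
| 6.0 | one | 42.5–64.2% | 1.038–1.127 |
| 6.0 | two | 5.4–9.8% | 1.004–1.012 |

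**5. One case written out** (placebo mean 4.4, SD 0.45, shift +0.2, cut 5.5, one decimal):
- Finerenone ≥5.5: 1 − Φ((5.45 − 4.6)/0.45) = 1 − Φ(1.889) = 2.945%. Placebo: 1 − Φ((5.45 − 4.4)/0.45) = 1 − Φ(2.333) = 0.982%. Difference 1.96 points.
- Finerenone >5.5: 1 − Φ((5.55 − 4.6)/0.45) = 1 − Φ(2.111) = 1.738%. Placebo: 1 − Φ((5.55 − 4.4)/0.45) = 1 − Φ(2.556) = 0.530%. Difference 1.21 points.
- Fall: 1 − 1.21/1.96 ≈ 38%. Risk ratio: 2.945/0.982 = 3.00 becomes 1.738/0.530 = 3.28.
- With 3000 per arm (half of the 6000 in SAP section 3), those at exactly 5.5 number 3000 × (2.945% − 1.738%) ≈ 36 on finerenone and 3000 × (0.982% − 0.530%) ≈ 14 on placebo.

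With two decimals the same case gives 2.336% vs 0.748% (≥5.5) and 2.216% vs 0.703% (>5.5). The difference moves only from 1.59 to 1.51 points, and about 4 and 1 participants sit at the cut.

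**6. Repeated visits.** The SAP comparison is any-time, not one visit. Taking the maximum of 10 visits in the same case, with an assumed within-person correlation of 0.3–0.5, the fall at 5.5 is about 31% with one decimal and about 3.5% with two. Neither model includes dose changes or the entry limit of 5.0 mmol/L.

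**The case against.** The strongest objection is that the governing protocol is unseen. SAP version 2.0, which logs the revision, is dated 24 FEB 2023, after the protocol of 26 OCT 2022 on which the SAP says it is based. Section 9.4.2 may have changed in between. A reader might infer that the SAP breaks with its protocol. The documents do not support that; they show only a mismatch with Amendment 2. This objection stands.

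Second, Amendment 2 does not use a single potassium cut. For an earlier finerenone study its Introduction has "Rates of hyperkalaemia defined as potassium" ≥5.6 mmol/L, which at one decimal is the same as >5.5. Section 4.3 mentions values above 6 mmol/L in a subgroup analysis. So a rationale for the strict cut may exist, but the SAP does not state one.

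Third, the protocol's own inclusive dosing guidance, "If potassium ≥5.5, down-titrate to the next lower dose level in a step-wise manner" in Table 6–1, could be taken to prove that the reporting cut must be inclusive. It does not. That guidance uses local values and the SAP tables use central ones. It shows only that the inclusive operator in the protocol is unlikely to be a slip.

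Fourth, the risk is reported in other ways: a >7.0 row, potassium summaries by visit, adverse events defined by a MedDRA grouping, hospitalisations, discontinuations and cumulative incidence. That is true and limits the consequence. None of these outputs supplies the two inclusive laboratory counts.

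**Conclusion.** The point holds as a minor one. Amendment 2 and the SAP attach the same two labels to different counts, the SAP tabulates neither Amendment 2 count, and the log does not explain the change.

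The direction is certain within each arm. The size is not. The falls of about 30–64% in the absolute difference need one-decimal central values and the assumed distributions; with two decimals they are about 3.5–10%. It would be tempting to conclude that the plan hides a third or more of the hyperkalemia signal. The documents do not support that: central precision is unstated, the model is illustrative, and the risk ratio is not understated in any scenario.

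The effect is confined to laboratory tables whose tests are explorative. The adverse-event analyses of hyperkalemia and all efficacy analyses are untouched.

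**What to change.** In SAP section 6.4.2:
- Add rows for serum potassium ≥5.5 and ≥6.0 mmol/L, labelled as the definitions in Amendment 2, section 9.4.2.
- Keep >5.5 and >6.0 as separate rows, without giving both sets the same label.
- Reconcile the label with the current protocol version: cite the version that changed the cut, if one did, and state the reason.

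The citation alone would explain the change but would leave the two Amendment 2 counts unreported, so the rows are the main part of the fix. The cost is two table rows from data already held, and reported rates that are slightly higher under the inclusive cut.

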6.4.3 Other Additional Safety Variables

6.4.3.1 Vital Signs

At the corresponding visits, 2 BP and 1 pulse measurements of vital signs parameters will be taken. Averages of non-missing values of these two BP measurements will be calculated and used for the statistical analysis. If only one of the planned measurements is available, this value will be used.

Vital signs values will be summarized by treatment group and visit using descriptive statistics including absolute changes from baseline. Changes from baseline will also be displayed graphically. The analysis will be repeated for SBP stratified by baseline SBP ≥ 90 to <130 mmHg, 130 to <160 mmHg and ≥ 160 mmHg.

6.4.3.2 Weight and BMI

The values and the changes from baseline will be summarized by treatment group and visit using descriptive statistics for weight and BMI.

6.5 COVID-19 and Related Issues

It is expected that the COVID-19 pandemic – ongoing at the start of the trial (14-Sep-2020) – will have some impact on this trial. Every effort will be made to capture the effect of COVID-19 on the study conduct. All adjudicated outcome events will additionally be adjudicated for relationship to COVID-19 (yes, possibly, no). COVID-19 related study disruptions comprise missing visits or procedures, study drug interruptions or permanent discontinuations, AEs related to COVID-19, and (other) protocol deviations and will be analysed as follows:

- All patients affected by study disruption related to the COVID-19 pandemic will be listed together with site information and the type of study disruption(s)
- Number of patients affected, number of missed visits, number and type of protocol deviations will be tabulated
- COVID-19 pandemic related reasons (participant decision, physician decision, or logistical reasons) for premature discontinuation of study epochs (e.g., screen failure, discontinuation of study drug, etc.) and changes in study treatment (e.g., dose titration, interruption, discontinuation, etc.) will be included in the relevant summaries
- Coded terms for COVID-19 will be included in medical history and adverse event summaries

Statistical Analysis Plan

Protocol No.: BAY 94-8862/20103

Page: 40 of 53

Supportive analyses to evaluate the impact of the COVID-19 pandemic on the primary analysis will be conducted for the primary and secondary efficacy endpoints.

The primary analysis of the primary and secondary endpoints mostly follows the treatment policy strategy as described in ICH E9 (ICH 2019), in which participants are analyzed as they were intended to be treated and all relevant data are used regardless of any previous intercurrent events like COVID-19 infections or study drug interruptions which could have an influence on the occurrence of the event of interest. Only the following intercurrent events are handled with different approaches:

| Endpoint | Intercurrent events and strategies |
|--|---|
| Primary endpoint (CV death and total HF events) | Non-CV death is treated as a censoring event for a while-alive strategy. Additionally, CV death is counted as both an outcome event as well as a censoring event, hence a combination of composite and while-alive strategy |
| Total HF events | Non-CV death is treated as a censoring event for a while-alive strategy. Additionally, the effect on total HF events is adjusted for a potential treatment effect on CV death |
| Improvement in NYHA class from Baseline to Month 12 | A composite strategy is applied when no measurement is available at Month 12 (due to death, or other reasons) |
| Change from baseline to Month 6, 9 and 12 in TSS from KCCQ | All observed values up to death for any cause are included, i.e. a while-alive strategy is used |
| Time to first occurrence of renal composite endpoint | All-cause death is treated as a censoring event for a while-alive strategy. If a participant had a decrease or decline in eGFR but died before a confirmatory eGFR measurement could be taken, then the event is counted for the analysis |
| Time to ACM | Not applicable |

This general approach is still considered valid despite the presence of the COVID-19 pandemic, considering the following factors:

- COVID-19 related study disruptions are expected to be equally likely to occur in either treatment group, therefore not creating bias for the treatment effect
- Information on most adjudicated endpoint events can still be collected even when physical visits cannot take place although incidences or reporting of some adjudicated events might change, e.g. as fewer participants might be hospitalized and have a higher risk of death

To quantify the impact of the COVID-19 pandemic, the following supplemental analyses will be performed:

- Primary endpoint (CV death and total HF events)
 - To address the hypothetical scenario in which participants did not experience any study disruption due to the COVID-19 pandemic, three separate analyses

will be conducted using the LWYY model described in Section 6.2.1.1 where participants are censored at

- a) Date of permanent discontinuation of study treatment due to COVID-19
- b) Date of first COVID-19 adverse event (SMQ narrow)
- c) Date of first direct or indirect COVID-19 study disruption

This analysis will be performed once including all primary efficacy events and once excluding those events adjudicated as related to COVID-19. For the latter analysis, the affected participants will be censored at the first occurrence of a COVID-19 related event

Additionally, plots and summaries of the mean cumulative function for the primary endpoint (Nelsen-Aalen estimate) will be presented by treatment group.

- To investigate the effect of COVID-19 related study disruption on the results of the primary analysis, a time-dependent covariate capturing whether a participant is affected by COVID-19 at the respective time together with its interaction with treatment group will be included in the LWYY model described in Section 6.2.1.1. Separate models will be used for the three COVID-19 related categories described above (permanent discontinuation of study treatment, AEs, and study disruption). Events occurring before and after participants are affected by COVID-19 will also be summarized by treatment group
- Primary efficacy events (CV death and HF events) and the competing event of non-CV death will be summarized by treatment group and relationship to COVID-19 as adjudicated by the CEC, defined as follows:
 - Yes (positive testing, typical clinical trajectory)
 - Possibly (inconclusive or absent testing, typical clinical trajectory)
 - No (testing negative or not done, not suspected)
- If $\geq 5\%$ of the total number of primary efficacy events are adjudicated as “Yes” or “Possibly” related to COVID-19, a further analysis using the LWYY model will be performed excluding such events; the affected participants will be censored at the first occurrence of a COVID-19 related event
- Primary efficacy events occurring during interruption of study treatment (due to COVID-19, or due to other reasons) up to 30 days after any temporary or permanent stop of study treatment will be summarized by treatment group
- Total HF events
 - Summaries of HF events occurring before and after participants are affected by COVID-19, and during interruption of study treatment, will be included as part of the summaries for the primary endpoint described above
- Improvement in NYHA class from Baseline to Month 12
 - Reasons for a participant being classified as “not improved” at Month 12 under the composite strategy will be summarized, including:

- NYHA measured at Month 12 and not improved from baseline
- NYHA not measured at Month 12 due to COVID-19 related reason
- NYHA not measured at Month 12 due to other reason
- Change from baseline to Month 6, 9 and 12 in TSS from KCCQ
 - No additional summaries or analyses are proposed. This endpoint will be analyzed by a repeated measures mixed model which is valid under the missing at random assumption, and COVID-19 related study disruptions are expected to be equally likely to occur in either treatment group and therefore not related to study treatment
- Time to first occurrence of renal composite endpoint
 - Events occurring before and after COVID-19 related study disruption, and during study treatment interruptions due to COVID-19 or other reasons, will be summarized by treatment group
- Time to ACM
 - To address the hypothetical scenario in which participants were not affected by the COVID-19 pandemic, the stratified log-rank test and stratified Cox proportional hazard model as described in Section 6.2.2.1 will be repeated excluding any death adjudicated as “Yes” or “Possibly” related to COVID-19; these participants will instead be censored at the date of death. Aalen-Johansen plots for non-COVID and COVID related deaths will also be displayed

